### **3.2. Independent Data Review Committee**

An independent data review committee (DRC) independent from the study team, will be established to monitor safety and efficacy data in an unblinded manner on a regular basis throughout the study and will make recommendations on treatment continuation for longer treatment durations to safeguard the health and the well-being of the study participants.

The details will be provided in a separate DRC charter and the selection of the required analysis outputs are indicated in a separated the DPS. The DRC output is a subset of the output included in the DPS of the final analyses.

## **4. SUBJECT INFORMATION**

All general analyses will be done on the ITT population unless specified otherwise for a specific display.

### **4.1. Disposition Information**

The following subject data will be tabulated:

- The number and percentage of subjects who are screened, screening failure and reason of that screening failure, as also the (not) randomized and (not) treated subjects. Only an all subjects group will be provided. This table does not have to be presented by

---

subject population and HBeAg status. The information on screening failures and not treated subjects is also listed for all subjects meeting the previous criteria.

- The number and percentage of subjects who completed or discontinued (or were ongoing for [only for interim analyses]) the study as documented on the study termination page and the number and percentage of subjects for each study discontinuation reason.
- The number and percentage of subjects who overall completed or discontinued (or were ongoing for [only for interim analyses]) the study agent as documented on the study drug termination page and the number and percentage of subjects for each study agent discontinuation reason. Further, the number and percentage of subjects who completed the initial 24 weeks treatment and treatment extension and information on participation in a treatment extension is included.
- The number and percentage of subjects randomized and treated for each analysis time point with information of the status of study participation at that particular analysis time point (i.e. ongoing, terminated study participation with the reason or completed).
- A listing including information (i.e. the date of last study visit, the last treatment period analysis time point, the date of discontinuation and the reason) on subjects which prematurely terminated the study and/or study agent is included.
- The overall date of first signed informed consent, first visit, last visit and last contact will be provided.

## **4.2. Demographics and Baseline Characteristics**

Tabulations of demographics, baseline characteristics and stratification factors will be presented for all subjects and by treatment group in the intent-to-treat population.

### **4.2.1 Demographic characteristics**

- Gender: Male, Female, Unknown, Undifferentiated
- Age (years)
  - Age (years) will use age at informed consent, if missing, age will be calculated as (date of informed consent – date of birth +1) / 365.25

---

- Age categories:  $\leq 45$  years,  $> 45$  years
- Race: American Indian or Alaska Native, Asian, Black or African American, Native Hawaiian or other Pacific Islander, White, Other and Unknown
- In case the subject is Asian provide subgroup: Asian Indian, Chinese, Filipino, Japanese, Korean, Vietnamese, Other, Multiple and Unknown
- Ethnicity: Hispanic or Latino, Not Hispanic or Latino, Not Reported
- Country
- Region: Asia /Non- Asia (Based on country according to UN classification of Geographic regions:  
[https://www.un.org/en/development/desa/policy/wesp/wesp\\_current/2014wesp\\_country\\_classification.pdf](https://www.un.org/en/development/desa/policy/wesp/wesp_current/2014wesp_country_classification.pdf))
- Height at baseline (cm)
- Weight at baseline (kg)
- Body mass index (BMI) at baseline ( $\text{Kg}/\text{m}^2$ ) = weight at baseline (kg) / (height at baseline (m)) (rounded to 1 decimal)
- Body mass index group: Underweight  $<18.5$ , Normal  $\geq 18.5-25$ , Overweight  $\geq 25-30$  and Obese  $\geq 30$
- Current smoker: Yes/No (Former smokers are included in the 'No' category)
- Subject population: Currently not being treated or virologically suppressed by current NA treatment: (SUPPDM.QNAM = 'SBVIRSUP')
- Hormonal contraceptive in females: Yes/No (only include for female subjects: SUPPDM.QNAM = 'FHORCONT')
- Type of Tobacco, Cigarettes, Cigars, Pipes, E-cigarette, Smokeless tobacco (listed only)
- Date of signing the Informed Consent (listed only)
- Date of birth (listed only)
- Childbearing potential (only listed)
- Alcohol test results (only listed)
- Drug testing results (only listed)

#### **4.2.2 Baseline characteristics**

For the viral activity parameters (e.g. HBeAg, HBsAg, HBV DNA), non-historical results are used unless specified differently.

---

- Mode of Infection: MSM, Heterosexual Contact, Intravenously Injectable Drug Use, Blood Transfusion, Hemophilia-associated Injection, Occupational Exposure, Mother to Child Transmission, Other, Unknown
- Last NA treatment before baseline: Lamivudine, Telbivudine, Adefovir, Tenofovir, Entecavir, IFN, Other:
  - The last historical NA treatment with indication in the FA dataset that the NA treatment is still used.
- Duration of infection (Years) = (date of baseline – date of HBV infection +1)/365.25; rounded to 1 decimal
  - Imputation rules for partially missing dates to calculate the duration are included in section 2.4.
- Time since diagnosis (Years) = (date of baseline – date of diagnosis+1)/365.25; rounded to 1 decimal
  - Imputation rules for partially missing dates to calculate the duration are included in section 2.4.
- Chronic Hepatitis B at screening: Chronic Hepatitis B as confirmed by a positive historical HBsAg status and a negative Hepatitis B IgM Antibody at screening.
  - Use the last available historical measurement for HBsAg: the qualitative result or the quantitative result. The quantitative result is positive when the result is higher than the quantification limit available in the dataset. If both are available at the same date use the quantitative result.
  - Use the last available measurement for Hepatitis B IgM Antibody before first study agent administration.
- Historical HBeAg status in virologically currently being suppressed subjects not being on NA treatment (LBHISTR = ‘N’). In case of multiple records available the latest prior to baseline should be used.
- HBeAg status at baseline (qualitative): Positive / Negative
  - Borderline is included as Negative
- HBeAg at baseline (quantitative: IU/mL and log10 IU/mL, for HBeAg positive qualitative results only): all samples are used, not only the quantitative counterpart of the qualitative result which is the same sample.
- HBsAg status at baseline (qualitative: IU/mL and log10 IU/mL): Positive / Negative
  - Borderline is included as Negative
- HBsAg at baseline (quantitative: IU/mL and log10 IU/mL): all samples are used, not only the quantitative counterpart of the qualitative result which is the same sample.
- HBsAg group at baseline
  - HBeAg positive currently not treated subjects
    - Subjects with HBsAg <10000 IU/mL

---

- Subjects with HBsAg  $\geq$ 10000 IU/mL
- All other
  - Subjects with HBsAg <1000 IU/mL
  - Subjects with HBsAg  $\geq$ 1000 IU/mL
- Historical HBV DNA at baseline (qualitative, based on historical data)
- HBV DNA at baseline (quantitative: IU/mL and log10 IU/mL)
- HBV DNA category at baseline (quantitative)
  - Subjects with HBV DNA < 20 IU/mL
  - Subjects with HBV DNA < 60 IU/mL
  - Subjects with HBV DNA < 2000 IU/mL
  - Subjects with HBV DNA < 20000 IU/mL
  - Subjects with HBV DNA  $\geq$  20000 IU/mL
  - Subjects with HBV DNA  $\geq$  100 000 IU/mL
  - Subjects with HBV DNA < 100 000 IU/mL
- HBV RNA (quantitative: copies/mL and log10 copies/mL)
- Hepatitis B core related antigen (HbcrAg) at baseline (quantitative: log10 IU/mL)
- HBV Surface Antibody (Anti-HBs) status at baseline (qualitative): Positive/Negative
- HBV Surface Antibody at baseline (quantitative: mIU/mL and log10 mIU/mL): all samples are used, not only the quantitative counterpart of the qualitative result which is the same sample.
- HBV e Antibody (Anti-HBe) status (Positive/Negative)
  - Borderline is included as Negative
- Alanine Transferase (ALT) at baseline (only Covance results)
  - Baseline ALT values (U/L))
  - Baseline ALT toxicity grade according to DAIDS
  - Baseline ALT categorization ( $\leq$  1.0 ULN, > 1.0 ULN - <2.5 ULN,  $\geq$  2.5 ULN)
  - Baseline ALT categorization ( $\leq$  1.0 ULN, > 1.0 ULN)
  - Baseline ALT categorization (<2.5 ULN,  $\geq$  2.5 ULN)
- HIV-1/2 AB / HIV-1 P24 AG Combo test (qualitative)

---

- Fibrosis Stage: F0, F1, F2, F3 and F4
  - Use the last available liver disease staging assessments performed by liver biopsy or fibroscan before first study agent administration should be used. If both results of liver biopsy and fibroscan at the same date, use the fibroscan result
- Method of liver staging assessment (Fibroscan / Biopsy) (listed only)
- HBV infection genotype/subtype (Coalesce): Genotype A, B, C, D, E, F, G, H, .., Unknown and Other
  - Use results from DDL Next generation Sequencing. If not available, use results from Covance Innogenetics Line Probe Assay method (Use for derivation of genotype)
- HBV infection genotype/subtype (Covance Innogenetics Line Probe Assay): Genotype A, B, C, D, E, F, G, H,..., Unknown and Other
- HBV infection genotype/subtype (DDL Next generation Sequencing): Genotype A, B, C, D, E, F, G, H,..., Unknown and Other
- HBV infection genotype/subtype (historical from FA domain): Genotype A, B, C, D, E, F, G, H,..., Unknown and Other
- HBV genotype (Coalesce) method: DDL Next generation Sequencing, Covance Innogenetics Line Probe Assay, Historical + method specified in dataset. (Use this genotype at baseline and listings only)

An additional listing will be provided representing any NA treatment prior to screening including drug type, start date of treatment, end date of treatment, an indication whether the drug is currently being used and reason for treatment discontinuation (FATESTCD = “REASDSC”).

---

#### 4.2.3 Randomization and stratification factors

The stratification factors found in IWRS are also found in the Electronic Case Report Form (eCRF):

- HBeAg status at screening (positive versus negative)
- HBsAg level at screening
  - HBeAg positive currently not treated subjects
    - Subjects with HBsAg <10000 IU/mL
    - Subjects with HBsAg ≥10000 IU/mL
  - All other
    - Subjects with HBsAg <1000 IU/mL
    - Subjects with HBsAg ≥1000 IU/mL
- Chronic Hepatitis B (CHB)-infected subject population
  - Currently not being treated
  - Virologically suppressed by current NA treatment (ETV or TDF)

The following randomization and stratification factor data will be tabulated:

- A cross-tabulation of the stratification factor HBeAg status and the HBeAg status at baseline/screening by treatment group. The number of subjects and percentages are shown. A totals column and row are included. This table does not have to be presented by subject population and HBeAg status.
- A cross-tabulation of the stratification factor HBsAg status and the HBsAg status at baseline/screening by treatment group. The number of subjects and percentages are shown. A totals column and row are included. This table does not have to be presented by subject population and HBeAg status.
- A tabulation of the stratification factors in the IWRS by treatment group. This table does not have to be presented by subject population and HBeAg status.
- A listing with randomization data (e.g. randomization date, number), stratification factors and randomized / actual treatment will be provided.

#### 4.2.4 Genotype/Subtype

Different methods of genotyping is used in the study. The following methods can be found:

- Covance Innogenetics Line Probe Assay (Inno LiPA)
- DDL Next generation Sequencing

The following tabulation about the different methods concerning genotypes will be provided:

---

- A cross-tabulation of the genotype (DDL Next generation Sequencing) and the genotype (Covance Inno LiPA) by treatment group will be provided. A total and missing, if applicable, column/row will be provided. This table does not have to be presented by subject population and HBeAg status.

#### **4.3. Protocol Deviations and Inclusion/Exclusion Criteria**

- Only major protocol deviations will be defined in this study. All major protocol deviations will be tabulated per coded term by treatment group.
- All inclusion criteria which were not met and exclusion criteria which were met are tabulated represented as inclusion/exclusion number.
- A listing of the major protocol deviation will be presented
- A listing of the deviations to the inclusion/exclusion criteria will be included
- A listing of the major protocol deviation coded as 'Received wrong treatment of incorrect dose' will be provided.

#### **4.4. Prior and Concomitant Medications**

All medications will be coded using the World Health Organization-Drug Dictionary. Tabulations will include prior and concomitant medications which are defined as follows:

- Prior medications are defined as medications with a start date occurring before date of first dose of study agent regardless of when dosing of the medication ended.
- Concomitant medications are defined as medications received at or after the first dose of the study agent, medication that was received before initial dosing and continued after initial dosing of the study agent, or medication with missing stop date.
- Medication that started before the first dose of study agent and continued after the first dose of study agent will be summarized as prior medication and separately as concomitant medication.
- In case of a completely missing start date, the concomitant therapy will be considered as having started before the trial or use all available information in the eCRF indicating if before or after or ongoing.
- In case of a completely missing end date, the concomitant therapy will be considered as ongoing at the end of the trial or use all available information in the eCRF indicating if before or after or ongoing.

All medication will be allocated to analysis phases taking into account their start date and end date as also the eCRF indication before or after or ongoing.

---

Concomitant medications of interest will be provided in this analysis. These will be determined by medical review of a distinct list of all coded concomitant medications and its Anatomical Therapeutic Chemical (ATC) class levels. The following categories will be included:

- Anti-HBV NA rescue medication (Nucleoside and nucleotide reverse transcriptase inhibitors)
- Any other types of rescue medication
- Oral contraceptives (hormonal contraceptive of systemic use)
- Medications that impact immune system (e.g. corticosteroids, cyclosporin, interferon)
- Medication that can be subject to CYP3A4 induction

The following tabulations and listings will be provided:

- Tabulation of the ATC level 2, ATC level 4 and preferred terms of the concomitant medications per treatment group and by analysis phase.
- Tabulation of the ATC level 2, ATC level 4 and preferred terms of the prior medications per treatment group and by analysis phase during which they were applied.
- Tabulation of the ATC level 2, ATC level 4 and preferred terms of the anti-HBV NA rescue medication (i.e. concomitant medications of interest) per treatment group and by analysis phase during which they were applied.
- Tabulation of the ATC level 2, ATC level 4 and preferred terms of any other types of rescue medication (i.e. concomitant medications of interest) per treatment group and by analysis phase during which they were applied.
- Tabulation of the category of the concomitant medications of interest and preferred terms of the concomitant medications of interest per treatment group and by analysis phase during which they were applied.
- A listing including all prior and concomitant medication (i.e. verbatim and coded term) with indication of prior/concomitant will be provided. All available data will be included as also ATC levels 2 and 4.
- A listing including the anti-HBV NA rescue medication and the any other types of rescue medication (i.e. concomitant medications of interests) will be provided. This listing will be similarly to the listing for prior and concomitant medication.
- A listing including all concomitant medications of interests will be provided similarly to the listing for prior and concomitant medication. This listing will be similarly to the listing for prior and concomitant medication except for an additional column for the concomitant medications of interest categories.

---

#### **4.5. Medical History**

A tabulation of the general medical history coded terms will be provided by body system class and by treatment group.

Listings including the general medical history, surgical medical history and family medical history will be included.

#### **4.6. Exposure**

The total duration of exposure of the study agent in weeks is calculated as follows:

$$(\text{last drug intake date} - \text{first drug intake date} + 1)/7$$

The following categories of total duration of exposure of the study agent are used in the analysis:

- < 1 week
- $\geq 1 - \leq 24$  weeks
- > 24 weeks

The following categories of cumulative total duration of exposure of the study agent are used in the analysis:

- $\geq 1$  week (i.e. also including all subjects included in the ' $\geq 24$  weeks' cumulative duration of exposure category)
- $\geq 24$  weeks

The following categories of adjustments of the study agent are used in the analysis:

- As study planned: No adjustments reported throughout the complete study
- At least one dose missed, reduced or increased: if any adjustments reported throughout the complete study.

The following tabulation and listings will be included:

- Descriptive statistics of the total duration of exposure of the study agent will be provided, as also the tabulation of total duration of exposure categories and cumulative total duration of exposure categories for all subjects, not by subject population and HBeAg status and using the safety population. Additionally, the descriptive statistics of the total duration of exposure for non-completed subjects (i.e. discontinued subjects and ongoing subjects [only for interim analyses]) and completed subjects will be presented separately.

---

- A cross-tabulation of the randomized and actual treatment arms are included. This table will not be presented by treatment group, subject population and HBeAg status.
- A tabulation of categories of adjustments of the study agent will be included. This table will not be presented by subject population and HBeAg status using the safety population.
- For every treated subject, the trial medications (i.e. study agent and NA treatment), their times of administration, as well as the corresponding doses and an indication whether a dose adjustment was present and the reason will be shown in a listing. Treatment administration on site and at home will be shown in chronological order.

#### **4.7. Drug Accountability and Compliance**

The compliance in this study is defined as the correct amount of tablets taken as there is no distinction made between the different doses of tables (i.e. 25mg or 100mg).

The percentage of compliance will be defined by the number of tablets that patients have taken during their duration of the study, assuming n tablets per day.

$$\text{Compliance (\%)} = \frac{\text{Number of tablets dispensed} - \text{Number of tablets returned}}{n * \text{number of day during the study}} * 100$$

Where n = 3 for part A (3\*25 mg=75mg) and n=4 for part B (2\*100mg + 2\*25mg=250mg)

Percentage of compliance will be summarized descriptively in the treatment phase and by discontinuing the trial during the treatment period

The treatment exposure and compliance will be summarized using the safety population by treatment group and for the treatment phase (including the extension follow-up phase) and for overall.

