### Part B:

Part B (ie, Treatment Arms 6 to 10) will follow the same format as Part A, with a different dose of JNJ-56136379.

Randomization in each part will be stratified by:

[figure not shown]
- HBeAg status at screening (positive versus negative);
- HBsAg level at screening ( $\geq 10,000$  versus  $< 10,000$  IU/mL for HBeAg-positive subjects currently not being treated and  $\geq 1,000$  versus  $< 1,000$  IU/mL for all other subjects).

The aim is to have approximately 40% HBeAg-positive subjects who are currently not being treated and 30% HBeAg-positive virologically suppressed subjects. To this end, enrollment of HBeAg-negative subjects may be capped at 60% in subjects who are currently not being treated and at 70% in virologically suppressed subjects.

A Data Review Committee (DRC) will be established for this study and will monitor safety and efficacy data in an unblinded manner on a regular basis throughout the study.

Part A will start first and will evaluate a 75-mg once-daily (qd) dose of JNJ-56136379. The JNJ-56136379 dose to be administered in Part B of the study will be 250 mg given once daily. This dose has been selected by the sponsor, in agreement with the DRC, based on all safety, PK, and antiviral activity data available following completion of the highest JNJ-56136379 dose group (who received 250 mg once daily) in the Phase 1 study 56136379HPB1001 in treatment-naïve CHB-infected subjects treated for 28 days.

Each part of the study will consist of a screening phase (up to 8 weeks), a treatment phase (24 weeks or 48 weeks, depending on treatment response), and a post-treatment follow-up phase (24 weeks or 48 weeks, depending on treatment response). A high-level overview of the study design is provided below.

a Per Protocol Amendment 4, subjects in the JNJ-56136379 250 mg monotherapy arm (Treatment Arm 6) who are eligible for treatment extension, based on the treatment extension criteria assessed at Week 20, will receive JNJ-56136379 in combination with NA treatment from Week 24 to Week 48.

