**Part B:**

Part B (ie, Treatment Arms 6 to 10) will follow the same format as Part A, with a different dose of JNJ-56136379 (see [Figure 1](#)).

Randomization in each part will be stratified by:

- HBeAg status at screening (positive versus negative);
- HBsAg level at screening ( $\geq 10,000$  versus  $< 10,000$  IU/mL for HBeAg-positive subjects currently not being treated and  $\geq 1,000$  versus  $< 1,000$  IU/mL for all other subjects).

The aim is to have approximately 40% HBeAg-positive subjects who are currently not being treated and 30% HBeAg-positive virologically suppressed subjects. To this end, enrollment of HBeAg-negative subjects may be capped at 60% in subjects who are currently not being treated and at 70% in virologically suppressed subjects.

A DRC will be established for this study (see Section [11.12](#)) and will monitor safety and efficacy data in an unblinded manner on a regular basis throughout the study.

Part A will start first and will evaluate a 75-mg once-daily dose of JNJ-56136379. The dose to be administered in Part B will be 250 mg given once daily. This dose has been selected by the sponsor, in agreement with the DRC, based on all safety, PK, and antiviral activity data available following completion of the highest JNJ-56136379 dose group (who received 250 mg once

daily) in the Phase 1 study 56136379HPB1001 in treatment-naïve CHB-infected subjects treated for 28 days. (For a rationale on dose selection refer to the Study Design Rationale below.)

Each part of the study will consist of a screening phase (up to 8 weeks), a treatment phase (24 weeks or 48 weeks, depending on treatment response), and a post-treatment follow-up phase (24 weeks or 48 weeks, depending on treatment response). For an overview of the study design, see [Figure 1](#).

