For subjects who continue treatment in the extension phase:

- Subjects will be considered to have completed the study treatment if they have completed 48 weeks of study drug administration, after which they will discontinue JNJ-56136379 or placebo treatment. At Week 48:

- Subjects who meet all of the Individual Subject Treatment Completion Criteria (see Section 6.3) will complete all treatment. These subjects will be followed-up until 48 weeks after EOT (Schedule 2). If, during the 48-week follow-up, a subject meets one of the re-treatment criteria described in Section 6.4, NA treatment (ETV or TDF) should be re-started.
- Subjects who do not meet the Individual Subject Treatment Completion Criteria should start (in case of JNJ-56136379 monotherapy, ie, Treatment Arms 1 and 6) or continue (in case NA treatment was part of the assigned study treatment, ie, Treatment Arms 2 to 5 and 7 to 10) NA treatment as per local treatment guidelines. These subjects will be followed-up until 24 weeks after the end of study treatment (Schedule 1).
- Subjects will be considered to have completed the study if they have completed the assessments of the end of study visit (FU Week 24 [Schedule 1] or FU Week 48 [Schedule 2]).
- For subjects who do not meet the Individual Subject Treatment Completion Criteria and do not start or continue NA treatment at Week 48, an additional 24-week follow-up (as per local treatment guidelines) by their primary care physician, outside of the study, is recommended after study completion.

The duration of individual participation will be up to approximately 56 weeks (subjects not eligible to continue treatment in the extension phase), up to 80 weeks (subjects continuing treatment in the extension phase but not meeting the treatment completion criteria), or up to 104 weeks (subjects meeting treatment completion criteria).

Efficacy will be evaluated through different measures (see Section 9.2).

Samples for HBV genome sequence will be taken at the time points indicated in the **TIME AND EVENTS SCHEDULE** (see Section 9.3). Sequencing of baseline samples will be performed by default if HBV DNA levels are within the ranges required for the sequencing assay. The sequencing of samples obtained after baseline may be triggered by the sponsor virologist based on changes in HBV DNA levels observed in each individual subject and the limits of the sequencing assay.

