## **2. GENERAL ANALYSIS DEFINITIONS**

The SAP will use throughout the document the following definitions:

- *Treatment* includes JNJ-56136379, placebo and NA (ETV or TDF)
- *Study agent* includes JNJ-56136379 and placebo
- *NA* includes NA (ETV or TDF)

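### The SAP's compliance denominator is worded as study days, not dosing days: read literally, a fully adherent planned completer scores 50% or 67% instead of 100%, which conflicts with the same section's treatment-phase summary.

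*SAP*

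**What the plan says.** SAP 4.7 defines compliance twice, and both times over the study. In words, it is based on "the number of tablets that patients have taken during their duration of the study, assuming n tablets per day". In the formula, the denominator is n (3 for Part A, 4 for Part B) multiplied by the "number of day during the study". Neither SAP 4.7 nor any other section defines that days term.

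The section then gives two statements about the summary period. One reads "Percentage of compliance will be summarized descriptively in the treatment phase". The other asks for exposure and compliance "for the treatment phase (including the extension follow-up phase) and for overall".

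The values of n match the number of JNJ-56136379 or placebo tablets per day, so the formula concerns study agent, which SAP section 2 says "includes JNJ-56136379 and placebo". NA tablets are not counted.

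The protocol separates finishing treatment from finishing the study. Under sections 3.1 and 10.1, JNJ-56136379 or placebo ends at Week 24 or Week 48, and the study is completed only at the follow-up Week 24 or follow-up Week 48 visit. The Time and Events footnotes for both follow-up schedules confirm that study agent has stopped by then.

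**The concern.** The numerator can grow only while study agent is being taken. If the denominator runs to the end of the study, the ratio falls through every follow-up week, however well the subject took the tablets. The size of the fall depends on the path: whether the subject entered the extension, met the treatment completion criteria, or stopped early.

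Two comparisons would be distorted:

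- **Across arms.** Arm 1 was stopped by sponsor decision and its subjects went into Schedule 1 follow-up. Those stopped before Week 24 would show lower compliance than equally adherent subjects in other arms.
- **Leavers versus completers.** SAP 4.7 also asks for compliance according to whether the subject left the trial during treatment. An adherent subject who leaves the trial while on drug has almost no off-drug days and scores close to 100%, while an adherent completer scores 50% or 67%.

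**Working it through.** The documents state no compliance percentage, so there is no figure to reproduce. The check applies the SAP 4.7 formula to a subject who takes every tablet.

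**Inputs**
- Formula and n: SAP 4.7.
- Treatment of 24 or 48 weeks (168 or 336 days), follow-up of 24 or 48 weeks, screening of up to 8 weeks: Protocol 3.1.
- End of the treatment phase at last study agent intake plus 5 days: SAP 2.3, Table 1.
- Dosing-day count (last intake date minus first intake date plus 1): SAP 4.6.

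**Formula.** With full adherence, tablets taken = n × T, where T is dosing days. For D denominator days,

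compliance = 100 × (n × T) / (n × D) = 100 × T / D.

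n cancels, so Parts A and B behave alike.

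**Results for planned completers**

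| Treatment + follow-up | Literal: Day 1 to end of study | Treatment phase (T + 5 days) | Dosing days |
|---|---|---|---|
| 24 + 24 weeks | 168/336 = 50.0% | 168/173 = 97.1% | 100% |
| 48 + 24 weeks | 336/504 = 66.7% | 336/341 = 98.5% | 100% |
| 48 + 48 weeks | 336/672 = 50.0% | 336/341 = 98.5% | 100% |

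**Variations on the literal reading**
- If the study is taken to begin with 8 weeks (56 days) of screening, the three values become 168/392 = 42.9%, 336/560 = 60.0% and 336/728 = 46.2%.
- A subject who stops study agent at Week w and completes 24 weeks of follow-up scores w/(w + 24). The documents give no individual stopping times, so w is an assumption: Week 8 gives 8/32 = 25.0%, Week 12 gives 12/36 = 33.3%, Week 20 gives 20/44 = 45.5%. The score is below 50% only if w is below 24.

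**The case against.** The strongest reply is that SAP 4.7 itself places the compliance summary in the treatment phase. A programmer who lets that sentence govern would limit the days accordingly and obtain 97.1% to 98.5%, a small error. No sentence states that follow-up days enter the denominator. In Table 1 the treatment phase consists of initial treatment and treatment extension, and follow-up is a separate phase. The bracketed words in the second summary statement may therefore simply mean the extension period, with follow-up a stray word. The SAP also uses overall elsewhere for pooling groups, so it need not mean Day 1 to end of study.

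Much of this stands. A reader might infer that the SAP never limits compliance to the treatment phase, or that it expressly includes follow-up. The documents support neither. Inclusion of follow-up follows only from the literal wording of the days term.

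What does not stand is that the summary sentence repairs the formula. It says where results are shown; it does not redefine the denominator, which is expressed in study terms both in words and in symbols. An overall figure is requested in addition to the treatment phase, and Table 1 contains no extension follow-up phase.

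A reader might also infer that a low percentage would be used to explain virological breakthrough or a lack of HBsAg effect. No passage plans this. Efficacy is analysed in the ITT population, no per-protocol set is defined, and compliance enters no efficacy model. Other evidence on adherence exists: exposure by dosing dates, dose-adjustment categories and a dosing listing in SAP 4.6, and the Week 16 pharmacokinetic sample added by Protocol Amendment 4 to assess compliance.

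**Conclusion.** The point holds as a defect in a stated formula, of minor consequence. Taken literally, SAP 4.7 gives a fully adherent planned completer 50%, 67% or 50% on the three planned paths. Those figures assume that days are counted from Day 1 to the end-of-study visit and that treatment and follow-up have their planned lengths. Adherent subjects who stop study agent before Week 24 and stay in follow-up, as some in Arm 1 may have done, would score lower. On the Table 1 treatment-phase reading the same completers score 97.1% to 98.5%; on dosing days they score 100%.

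The text does not settle which of these will be programmed, so it cannot be said that adherent subjects will be reported at 50% to 67%. The literal formula and the treatment-phase summary conflict and should be reconciled. Because compliance is only descriptive, no efficacy conclusion depends on it. A reader might conclude that an overall compliance figure should be dropped; that does not follow, because it is valid once the denominator is corrected.

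**What to change.** In SAP 4.7:

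1. Replace the days term, in the formula and in the verbal definition, with date of last study agent intake minus date of first study agent intake plus 1, as in SAP 4.6, restricted to the period summarised: initial treatment, treatment extension, or both combined as overall.
2. Count tablets dispensed and returned over the same period. For subjects entering the extension, tablets and days need a common cut point. The Week 24 visit, when study agent is dispensed for the extension, is the natural one, because the Table 1 boundary lies 5 days after the Week 24 intake.
3. Replace the words extension follow-up phase with treatment extension period.

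The cost is one formula, its verbal definition and one phrase. It needs no new data and no change to trial conduct.
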